### 2. Design

This trial will use a between-subject single blind design in which participants will be randomized to one of three tDCS dosage groups (1mA, 2mA or sham) and will receive three 20 minute sessions of the same dosage over the course of 1 week before completing a 7 day quit attempt. Eligible participants will complete an **Intake Visit (week -1)** for final eligibility determination, and complete baseline measures (if eligible). Participants will then be randomly assigned to one of the three dosage groups (1mA, 2mA or sham) and will attend **three identical tDCS resist-smoking sessions (study days 1, 3, & 5)** during which they will receive 20 minutes of their assigned tDCS dosage and complete a resist smoking paradigm. During the resist smoking sessions, participants will receive a session of their assigned dosage of tDCS for 20 minutes while being exposed to in vivo smoking cues (their cigarette pack, cigarettes, an ashtray). Participants will not be informed of their dosage condition. During and after the tDCS session, participants will have the opportunity to smoke in the approved smoking lab. We will measure time to first cigarette and subsequent ad-libitum smoking during the resist smoking paradigm. Following Session 3 participants will receive a 20 minute coaching session from a trained smoking cessation counselor to help them prepare for a **7-day quit attempt**. During the 7-day quit attempt participants will be asked to attend **4 monitoring visits (study days 6, 8, 10 & 12)** to confirm smoking status.

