### 1. Screening/Covariates:

**Urine Pregnancy Test (females only):** At the Intake and Session 1-3 visits (4 urine pregnancy screens total), participants will be supplied with a simple, CLIA-waived urine pregnancy screen and informed that pregnant women are not advised to participate in this research study. Participants will then be instructed to administer the pregnancy test independently and will inform study staff if they would like to continue participation after they have administered the pregnancy screen. Participants will be informed that there is no penalty for discontinuing participation at this point in the visit and that they will still receive travel reimbursement for the visit.

**Breath Alcohol Concentration:** The BrAC assessment will be administered at all study visits. The breath alcohol monitor is a handheld device that uses a disposable mouthpiece and reports the concentration of alcohol in exhaled breath. Any reading > 0.000 indicates alcohol consumption within the last 14 hours. Participants with a BrAC greater than or equal to 0.01 at the Intake Visit will be ineligible. Participants who have a BrAC reading greater than or equal to 0.01 at either tDCS visit may be ineligible to continue with the visit and will only be rescheduled/allowed to proceed with the study at the discretion of the Principal Investigator.

**Demographics:** Standard surveys will collect demographics (e.g., age, education, race, and gender).

**Medical:** Height and weight will be measured and recorded. All participants will complete a medical history form with a trained staff member to review for all contraindications listed previously.

**Shipley Institute of Living Scale:** All participants will complete the Shipley Institute of Living Scale (SILS) at the Intake Visit. The scale consists of two subtests: a 40-item vocabulary test and a 20-item test of abstract thinking. The total administration time is 20 minutes (10 minutes per subtest). A trained member of the study staff will score

2012; Roche et al., 2014). Similar models were used to estimate the effects of dose group on total number of days of biochemically-verified abstinence during the monitored abstinence period; age, sex, race, and nicotine dependence (FTND score) were included as covariates.

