We conducted a futility analysis based on conditional power (futility = conditional power <20%) using results from the mixed model with dose of 1mA and 2mA lumped. Conditional power was calculated using PASS v15 (Power and Sample Size, NCSS Software, Kaysville, UT). Conditional power is the probability of rejecting the null hypothesis given the data already revealed; data that have not been revealed yet are assumed to follow the original assumed effect size. We used the z-score for the comparison of sham with lumped active treatment ( $z=0.04$ ,  $p=0.96$ , effect size=0.01), combined with the original design effect size of  $d=0.45$ . Conditional power was 0.13, indicating that the study should be abandoned for futility (Proschan et al., 2006).

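### Does a conditional power computed for the two active doses pooled leave the futility conclusion unsupported for each dose?

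*Combined protocol and SAP*

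**What the plan says.** Study Design, section 2 (Design), states that "participants will be randomized to one of three tDCS dosage groups (1mA, 2mA or sham"), and Table 1 lists the same three conditions.

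The futility paragraph stands just before section 2 (Confidentiality). Its rule is "futility = conditional power <20"%. It identifies the contrast twice: the calculation was made "using results from the mixed model with dose of 1mA and 2mA lumped", and "We used the z-score for the comparison of sham with lumped active treatment". The inputs are z=0.04, p=0.96 and an observed effect size of 0.01, with a design effect of d=0.45 for the rest of the trial: "data that have not been revealed yet are assumed to follow the original assumed effect size". It ends: "Conditional power was 0.13, indicating that the study should be abandoned for futility".

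The sentence that closes the preceding paragraph reads: "Similar models were used to estimate the effects of dose group on total number of days of biochemically-verified abstinence". What comes before it is lost. Section 1 (Screening/Covariates) breaks off in the description of the Shipley scale, and the text resumes at the tail of a citation list.

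**The concern.** In a three-arm trial, the mean of two active arms can hide a difference between them. With equal arms and equal variances, the pooled statistic is fixed by the sum of the two dose-versus-sham statistics and says nothing about the gap between them. A pooled z near zero could come from two inert doses, or from one dose above sham and one below. The conclusion is worded for the whole study, and no dose-versus-sham estimate, z or conditional power stands beside it. If one dose were promising, a pooled futility figure could end the study of both, and a reader could not see this from the paragraph.

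**Working it through.** **Inputs from the futility paragraph.** Pooled z=0.04, p=0.96, effect size 0.01, d=0.45 for the remaining data, conditional power (CP) 0.13, threshold 0.20.

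**Assumptions, because the available text gives no value.** Allocation 1:1:1; 5% alpha; pooled design power of 80% or 90% at d=0.45. A third case replaces the power assumption by the standard error implied by the text, 0.01/0.04 = 0.25. Two-sided testing is supported by the text: z=0.04 gives a two-sided p of 0.968, and z=0.045, which is within rounding, gives 0.964. A one-sided p would be about 0.48.

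**Step 1: the plan's own figure.** With information fraction t, drift θ and critical value c,

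CP = Φ[(z√t + θ(1−t) − c)/√(1−t)], plus a negligible opposite tail.

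The available text does not give t, so 0.13 cannot be reproduced outright. One can solve for the t that returns it. For 80% power, θ = 1.960 + 0.842 = 2.802, and t = 0.574 gives (0.030 + 1.194 − 1.960)/0.653 = −1.126, so CP = 0.130. The other cases give t = 0.619 (90% power, θ = 3.242) and t = 0.531 (SE 0.25, θ = 2.471). These are ordinary interim fractions, so 0.13 is plausible.

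**Step 2: what the pooled z implies for each dose.** Under 1:1:1 allocation, z_pooled = (z_1mA + z_2mA)/√3, so the two dose statistics sum to 0.04 × √3 = 0.069. Taking d=0.45 for each dose in the remaining data, the drift for a single dose is θ√0.75. If the doses behave alike, each z is 0.035. For 80% power, θ√0.75 = 2.426, and at c = 1.96 the argument is (0.026 + 1.034 − 1.960)/0.653 = −1.378, so CP = 0.084. At a Bonferroni value of 2.24 it is 0.035.

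**Step 3: how easily one dose reaches 20%.** Given the pooled z and no true dose difference, z_1mA − z_2mA has mean 0 and variance 1. One dose therefore reaches a threshold z* with probability 2[1 − Φ(2(z* − 0.035))].

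| | c = 1.96 | c = 2.24 |
|---|---|---|
| CP of each dose if alike | 0.08-0.09 | 0.03-0.04 |
| z* at which one dose reaches 20% | 0.47-0.52 | 0.83-0.91 |
| z of the other dose at that point | −0.40 to −0.45 | −0.76 to −0.84 |
| Chance of this by noise alone | 33-38% | 8-11% |
| Current-trend CP of a dose just at z* | 0.01-0.04 | 0.03-0.07 |

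Ranges cover the three cases. The available text gives neither a per-dose critical value nor any sign of whether d=0.45 was a pooled or a per-dose design effect. Whether a per-dose CP would be reassuring or noisy therefore depends on a choice made outside the plan.

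**Step 4: evidence against a hidden active dose.** If one dose had a true effect of 0.45 and the other none, the pooled mean would be 0.225. With a pooled interim standard error of 0.212, 0.176 or 0.250, the chance of a pooled z of 0.04 or less is Φ(0.04 − 0.225/SE) = 0.15, 0.11 or 0.19.

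**Step 5: what the text claims.** The paragraph names the pooled contrast when it introduces the model and again when it gives the z-score. It says nothing about 1 mA alone or 2 mA alone. Describing 0.13 as a pooled figure would only repeat what is there.

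**The case for a change.** The strongest case for the concern is that 0.13 cannot establish futility for each dose, and that a reader of a trial with three dosage groups will want to know. If the doses truly differed by 0.45, one of them would reach 20% in 43-73% of interims at c = 2.24, and more often at 1.96. A refit with dose at three levels would be cheap, and if both values fell below 20% the sponsor could say that futility holds for both doses.

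The algebra stands: the pooled z does not determine the dose-specific values, and the futility paragraph gives none. The rest is weaker. The plan does not assert futility dose by dose, so it makes no overclaim that needs correcting. The missing values may lie in the lost text; the reference to similar models for dose group suggests that the primary model also used dose group. A dose that only just reaches 20% would do so because the remaining data are assumed to follow d=0.45; on its current trend its conditional power would be 0.07 or less, with the other dose observed below sham. Computed after the stop, such a figure is easily misread.

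**Conclusion.** The concern does not hold. The futility analysis names its contrast, applies its own 20% rule to it, and reaches the conclusion that 0.13 supports: the pooled active-versus-sham comparison was unlikely to succeed. Nothing in the text extends that figure to a single dose. That one paragraph lacks per-dose values does not show that the plan lacks them, because the adjacent primary-model text is missing from the file.

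If the doses act alike, each is futile too, with conditional power between 0.03 and 0.09. The chance of a spurious pass for one dose ranges from 8% to 38% according to the critical value chosen. These figures assume 1:1:1 allocation, 5% two-sided alpha, and 80-90% pooled power or a standard error of 0.25. The verdict rests on the wording of the futility paragraph and on the gap in the text, not on these assumptions. Per-dose conditional power would be an optional extra; neither the pooling nor the decision to stop is shown to be wrong.

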## **2. Confidentiality**

Confidentiality of the data generated in this study shall be maintained in the following ways:

- Paper-based records will be kept in a secure location and only be accessible to personnel involved in the study.
- Computer-based files will only be made available to personnel involved in the study through the use of access privileges and passwords.
- Prior to access to any study-related information, personnel will be required to sign statements agreeing to protect the security and confidentiality of identifiable information.
- Whenever feasible, identifiers will be removed from study-related information
- Any study communications made by e-mail will use ID numbers only and never include names or any other personal information
- Audio and/or video recordings will be transcribed and then destroyed to eliminate audible/visual identification of subjects.
- Biological samples will be de-identified, labeled with a study ID number, and stored in our private bank. The sample bank is accessible to study staff only, and is located within our Center at [name].

Confidentiality of the data generated in this study shall be maintained in the following ways. First, all participant information/files will be kept in a secure filing cabinet that is accessible only to authorized study personnel. Second, all databases containing participant information will be password protected, and again, accessible only to authorized study personnel. Third, any study communications made by e-mail will use ID numbers only and never include names or any other personal information. Fourth, in all data sets we will use ID numbers only. A separate data set subject map table linking names with ID numbers will be accessible only by authorized personnel.

Since self-report and biological data will be collected and stored as part of this study, it is possible that subject privacy or confidentiality can be threatened. To address this concern, the data management system has set up several safeguards to prevent unauthorized access to study data. In the subject map table, an automatically generated index number is assigned to a subject's study identification number. A linked subject identification table is created to store subject name, address, and telephone contact information. This table uses the automatically generated index number rather than the study identification number. The master subject map and subject identification information are maintained in separate locations. Using this method, no identifying subject information is directly linked to bio-samples or results. Any publication of data will not identify participants by name or with an identifier that could be used to reveal identity.

All biological samples will be labeled with study ID only. All subject data that can be linked to the study ID will be stored in the secure data management system, which has limited, password-required access. Additionally, biological samples will be stored in our private sample bank which is locked at all times and is accessible only to the research team.

The aforementioned precautions and procedures will be applied to protecting subject privacy and the protected health information detailed in Section 4 below.

## **4. Subject Privacy/Protected Health Information**

The following protected health information (PHI) may be collected as part of this study:

1. Name
2. Street address, city, county, zip code
3. All elements of dates (except year) for dates directly related to an individual and all ages over 89
4. Date of birth
5. Social Security Number
6. Telephone number
7. Email address
8. Results from all questionnaires, tests, and procedures
9. Saliva sample for nicotine metabolite and genetic analysis
10. Any other unique identifying number, characteristic, or code
11. Video recordings of smoking sessions including the participant's face

Potential participants will be contacted over the phone after responding to recruitment advertisements. Participants will undergo an initial phone screening where preliminary eligibility for the research study will be determined. Only if a participant is initially eligible, will they attend an in-person Intake Visit to confirm eligibility. All data collected over the phone and during in-person visits will be collected by research staff that have completed the CITI Protection of Human Subjects Research Training as well as HIPAA Compliance Training. Information will never be recorded with identifiers other than study ID. A separate list of names with ID numbers will be accessible only by authorized personnel. All records will be kept in locked filing cabinets to maintain confidentiality. Results will not be communicated to other personnel or to the subjects. All analyses will be conducted on de-identified data. Data will be accessible to the Study Investigators, Study Physician, study staff, UPenn IRB, Office of Clinical Research, authorized UPenn staff (e.g. accounting and billing matters, provide treatment, etc.) and the Food and Drug Administration. Video recordings of participants will not include other identifying information other than their face, such as name. Recordings will be kept on password protected computers accessible to study specific staff only. Recordings will be destroyed one year after study completion after data has been reviewed and verified.

## **5. Tissue Specimens**

Saliva: A 2ml saliva sample will be collected for DNA extraction using the Oragene™ kit at the Intake Visit for genetic analyses. An additional saliva sample (~ 5ml) will be collected at the Intake Visit to analyze nicotine metabolites.

Urine: Urine (~30ml) will be collected at the Intake Visit to conduct a urine pregnancy screen (females only). A urine pregnancy screen (females only) will be required at all study visits.

## **6. Genetic Testing**

All genetic information (as with all study information) will be kept strictly confidential using the procedures outlined in Section 3, above. Results will not be revealed to study participants.

## **RISK/BENEFIT ASSESSMENT**

### **1. Potential Study Risks**

The potential risks to participants, and their likelihood and seriousness, are described below. Participants can choose, as an alternative, to not enroll in this study. Overall, there is minimal risk for serious adverse reactions as a consequence of enrolling in this study. Adverse reactions will be assessed and reported as required by Federal law and UPenn regulations.

tDCS: The animal literature regarding the safety of direct current stimulation of the brain was reviewed by Agnew and McCreery (Agnew and McCreery 1987) and McCreery and others (McCreery, Agnew et al. 1990). Based on these reviews, as well as their own work with humans, Nitsche and colleagues (Nitsche, Liebetanz et al. 2003) published a comprehensive review of the safety of tDCS. Citing animal research, they argue that the major variables relevant to safety in humans are current density and total charge. Current density is calculated as the current strength/electrode size. Assuming electrode sizes of 25 cm^2 (the standard electrode size with the neuroConn Channel-DC Stimulator Plus unit), the current density that would be generated by a 1 mA current is .04 C/cm^2; the current density generated by a 2.0 mA current is .08 mA/cm^2. McCreery and colleagues (McCreery, Agnew et al. 1990) demonstrated that current densities below 25 mA/cm^2 were not associated with evidence of tissue damage. The maximum current density that we propose to employ is 1/312 the level that was

considered to be safe in animals; additionally, this current density is similar to that employed by other investigators in the field.

Total charge in this context refers to the total amount of current that passes through the skin in the course of the study. It is noteworthy that the current delivered to the brain is estimated to be approximately 50% that delivered to the skin. Total charge is calculated as the current strength/electrode size x stimulation duration. McCreery and colleagues (McCreery, Agnew et al. 1990) reported that the lowest total charge at which tissue damage was recorded in animals was  $216 \text{ C/cm}^2$ . Assuming the maximum current that we propose to employ (2.0 mA) for the maximum duration that we propose to employ (20 minutes), the total charge to which our participants would be subjected is  $0.096 \text{ C/cm}^2$ , an amount that is  $1/2250$  of the minimum total charge that generated detectable changes in animals. The safety of tDCS has been addressed in a number of manuscripts. As described by Nitsche et al (2003), studies have demonstrated that using current densities of up to  $0.02875 \text{ mA/cm}^2$  and total charges of up to  $0.022 \text{ C/cm}^2$ , there is no heating under the electrode, no increase in neuron-specific enolase (a marker of neuronal injury), no changes in diffusion weighted or contrast-enhanced MRI and no abnormalities on EEG. Additionally, Nitsche and colleagues (Nitsche, Niehaus et al. 2004) reported that tDCS protocols that were shown to produce effects lasting for an hour were not associated with abnormalities on T1, T2 or diffusion-weighted MRI performed 30 and 60 minutes after stimulation.

A second study exploring the safety of the technique was reported by Iyer and colleagues (Iyer, Mattu et al. 2005). These investigators report experience with 103 subjects from age 19-70 (mean  $37.5 \pm 12.9$ ); half of the participants received sham treatment. In this study, a current density of  $40 \text{ microA/cm}^2$  for 20 minutes was administered to approximately 36 participants and a current density of  $80 \text{ microA/cm}^2$  was used for 15 participants. One electrode was placed over the left frontal region and the other over the right supraorbital region. EEG was recorded in 9 participants. No participant asked to stop the protocol and no participant reported significant pain. Some participants noted mild tingling at the electrode site. Minor redness was noted under the electrode site in two men who had recently shaved their heads. Cognitive function was assessed before and after stimulation. With  $80 \text{ microA/cm}^2$  current density a significant improvement in verbal fluency was observed with anodal stimulation but not in the sham or cathodal stimulation groups. A battery of neuropsychological tasks was administered to screen for adverse effects. No adverse effects were found for any measure of cognitive performance.

Finally, Poreisz and colleagues (Poreisz, Boros et al. 2007) reported on their extensive experience (567 sessions) with tDCS to multiple brain regions in 102 healthy participants and patients. None of the participants asked for a session to be terminated or required any medical assistance. For this study all participants completed a questionnaire inquiring about potential adverse effects. The questionnaire included assessment of headache, difficulties in concentrating, mood changes, visual perceptual changes and uncomfortable sensations (e.g., tingling, burning). Responders included healthy participants (75.5%), migraineurs (8.8%), post-stroke patients (5.9%) and patients with tinnitus (9.8%). A mild tingling sensation was the most common symptom, occurring in 71% of participants; the mean rating of the tingling was  $1.74 \pm 0.84$  on a 1-5 scale. Moderate fatigue was noted in 35% of participants during but not after the stimulation; the mean rating was  $2.17 \pm 1.11$ . Itching under the electrode was reported by 30%; the mean rating was  $1.6 \pm 0.72$ . Burning was reported by 22% and pain by 16% but, once again, both were regarded as quite mild ( $1.59 \pm 0.91$  and  $1.41 \pm 0.71$ , respectively).

There have been no significant side effects noted in any study involving tDCS to date. That is to say that in the approximately 300+ studies that have been published to date there have been no reported seizures, loss of consciousness or persistent neurologic signs or symptoms. Moreover, there have been 15 studies in which tDCS has been administered to stroke patients, again with no significant side effects. These data are in accord with our collaborator laboratory's observations. In the approximately 200 sessions [name] laboratory has performed with normal healthy participants there have been no significant side effects. In short, all existing evidence indicates risks posed by tDCS are non-significant. In the unlikely event that either the participant or the person administering tDCS has significant concerns, the participant will be escorted to the Emergency Room if a physician involved with the study cannot be contacted immediately. A physician involved with the study will then contact the participant within 24 hours to follow up.

All personnel using tDCS will be properly trained in the research protocol to ensure safe handling of the equipment. The training protocol includes hands-on training, written examination, mandatory observation of tDCS delivery and mandatory administration of tDCS under observation by a trained staff member.

**Nicotine Withdrawal:** Many individuals who stop smoking exhibit a pattern of symptoms related to withdrawal from tobacco use. These symptoms include: sadness and anxiety, irritability, anger, difficulty concentrating, appetite change and weight gain, insomnia, and decreased heart rate. Eliminating the risk for these would not be possible, although in most cases these events are short-lived and have low intensity. The study personnel will be trained to recognize these symptoms and educate the participants about them (e.g., duration, methods for reducing them).

**Email Communications:** In this research study participants may prefer to receive appointment reminders via email or submit questions related to study logistics. Email is not a secure means of communication. Email messages travel across the Internet passing through multiple computers before reaching their final destination. It is not possible to know whether an email a participant sends will be viewed along the way. Additionally, if sent messages are not deleted, an email provider may have an archive of everything that is sent. If someone gets access to an email account (for example, a participant's family member), they could see archived messages. There are many other ways in which emails are not secure—these are only selected examples. To manage this risk the informed consent form will include specific language to educate research participants on the privacy risks involved in email communications. Participants will also be explicitly instructed to only use email communications for routine matters and never for personal or confidential messages or questions.

**Video Recordings:** Video recordings will be made of participant smoking sessions during Sessions 1-3 for the purpose of verifying number of cigarettes smoked during a session and latency to smoke. Video recordings of participants will not include other identifying information other than their face, such as name. Recordings will be kept on password protected computers accessible to study specific staff only. Recordings will be destroyed one year after study completion after data has reviewed and verified.

**Genetic Testing:** All genetic information (as with all study information) will be kept strictly confidential using the procedures outlined in section 3 (Confidentiality), above. Results will not be revealed to study participants.

**Threats to Privacy/Confidentiality:** See description in Section 3 (Confidentiality) and 4 (Subject Privacy/Protected Health Information) above.

